# Hypotheses

It is hypothesised that:

- i. Those who walk the furthest will have lower exertional dyspnea scores during the 6MWT.
- ii. Exertional dyspnea will increase with an increase in gradient of the dyspnea challenge.
- iii. There will be differences between the two tests; there will be no-steady state response in the dyspnea challenge when compared to the 6MWT, a higher peak VO2 response and a marked difference in oxygen saturation.
- iv. The dyspnea challenge is able to detect both acute and longer term changes in exertional dyspnea as a result of interventions.

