#### Part B:

Visit 4-6 – During these visits' participants will perform 6xDC at various gradients of between 3-8% at a speed of 1.5km/h as above. These will be performed in a randomised order. During each test ECG, Q (PhysioFlow, Manatec Biomedical, Paris, France), HR and SpO2 (RAD-5v Masimo Corp, Irvine, CA, USA) will be monitored continuously throughout the test. Ratings of ED will be participant self-reported every 10 seconds using a 0-10 Numerical Rating Scale (NRS) on a PC-based system with a computer monitor mounted in-front of the treadmill. At the end of each test, as per previous tests, the MDP will be completed to assess the sensory and affective components of ED.

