## f. Data Analysis

As subjects act as their own controls, a repeated measures Analysis of Variance statistic will be used for quantitative (physiological) data. All tests will be of a 2-within factor design: time and experimental condition. Dyspnea scores will be measured in the same way. Any non-normal distributed data, highlighted by variance ratio tests, will have a non-parametric Kruskal-Wallis test being applied. Post-hoc analysis will be conducted on any statistically significant data identified post study. Questionnaire data will be analyzed using a Wilcoxon signed rank test. For other comparisons, descriptive statistics alone will be used. Data may be further explored using appropriate parametric or non-parametric correlation statistics. All statistical tests will be done with SPSS software with a significance threshold of P<0.05.

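### Part B: the Wilcoxon signed rank test named for questionnaires does not fit MDP scores taken at six gradients, and the omnibus ANOVA for the dyspnea rating does not use the order in hypothesis ii

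*Protocol*

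**What the plan says.** Hypothesis ii is ordered: "Exertional dyspnea will increase with an increase in gradient of the dyspnea challenge". In Part B, "participants will perform 6xDC at various gradients of between 3-8" per cent, in randomised order, with a 0-10 rating every 10 seconds. On the MDP, Part B adds: "At the end of each test, as per previous tests, the MDP will be completed". Outcome Measures places the MDP under the primary outcome and describes 11 items in three subsections. Part C refers to the MDP and the TDI together as questionnaires.

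The Data Analysis section then sets four rules that bear on Part B:

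- For physiological data, "a repeated measures Analysis of Variance statistic will be used for quantitative (physiological) data", and dyspnea scores are handled the same way. The structure is fixed: "All tests will be of a 2-within factor design: time and experimental condition".
- "Post-hoc analysis will be conducted on any statistically significant data identified post study".
- "Questionnaire data will be analyzed using a Wilcoxon signed rank test".
- "All statistical tests will be done with SPSS software with a significance threshold of P<0.05".

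The section names no trend contrast, slope or adjusted significance level, and does not say which gradients the questionnaire test would compare.

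**The concern.** Two separate things are wrong for Part B.

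First, the test named for the MDP handles two paired conditions and Part B has six. It can be applied only by picking pairs, and the protocol neither limits the pairs nor puts an overall test in front of them. Its other non-parametric option, Kruskal-Wallis, is for independent groups, so it does not fill the gap for repeated measurements on the same people. At stake is the false-positive rate of a primary outcome measure.

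Second, the question for the dyspnea rating is whether it rises with gradient. An omnibus ANOVA asks only whether the gradients differ somewhere. It spends five degrees of freedom on a question that needs one, and gives no estimate of dyspnea units per 1% gradient, which is the natural measure of the sensitivity named in primary aim ii.

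**Working it through.** The protocol gives no power, effect size, SD or error rate, so there is no figure of its own to reproduce.

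**Inputs from the protocol.** Six Part B tests, read as six distinct gradients (3, 4, 5, 6, 7, 8%); 30 participants per disease, 90 in all; significance at 0.05. **Assumed:** two-sided tests, equal correlation between gradients, no dropout, the time factor averaged out, and the effect sizes below.

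**1. False positives with pairwise Wilcoxon tests.** Number of pairs: 6 × 5 / 2 = 15. If the tests were independent, the chance of at least one false positive would be 1 − 0.95^15 = 53.7%; for five tests, 1 − 0.95^5 = 22.6%. Pairs share data, so the true figures are lower. They were simulated with no gradient effect, at n = 30, 60 and 90, with continuous, 0-10 integer and floor-limited scores (10,000 to 20,000 runs each):

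- all 15 pairs at 0.05: 37.6-38.5%
- five adjacent pairs: 20-21%
- five comparisons with the lowest gradient: 18-19%
- all 15 pairs at 0.05/15 = 0.0033: 2.5-4.2%
- one linear slope test: 4.6-5.4%

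As a cross-check, the studentized range distribution for 15 unadjusted pairwise t-tests gives 36-37%.

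**2. Post-hoc tests after a significant ANOVA.** In the same simulations, testing pairs only when the ANOVA is significant gives 4.7-5.3% when no gradient differs. If one gradient clearly differs and five are equal, the gate is passed and unadjusted tests among those five give about 28% (studentized range, five means).

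**3. Power for a straight-line rise.** Let D be the total rise from 3% to 8% in within-person residual SD units. With equally spaced gradients the squared deviations sum to 0.7 × D², so the noncentrality is λ = n × 0.7 × D². The ANOVA uses a noncentral F with 5 and 5(n−1) df; the per-person slope uses a noncentral t with n−1 df and noncentrality √λ. For n = 30:

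| D | λ | Omnibus ANOVA | Slope |
|---|---|---|---|
| 0.5 | 5.25 | 37% | 60% |
| 0.6 | 7.56 | 52% | 76% |
| 0.75 | 11.81 | 74% | 91% |
| 1.0 | 21.0 | 96% | 99% |

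For 80% power the slope needs 47, 34 and 22 participants at D = 0.5, 0.6 and 0.75; the ANOVA needs 75, 53 and 34.

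**4. If slopes differ between people.** At n = 30 and a mean slope of 0.12 SD per 1% gradient (5 × 0.12 = 0.6 in total), simulated power for slope against ANOVA is 76% vs 52% with no variation, 69% vs 49% with a between-person slope SD of 0.1, and 52% vs 43% with 0.2.

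**The case against.** The Wilcoxon sentence may be meant for two-condition comparisons, such as with and without the binder or before and after rehabilitation, where it fits. MDP results are also dyspnea scores, so the ANOVA sentence could be read to cover them. Both readings are possible, but the protocol does not restrict the Wilcoxon rule, calls the MDP a questionnaire, and collects it at every Part B gradient. As written, the rule reaches Part B.

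A reader might go further than the protocol allows in four ways:

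- *That about 38% is the trial's false-positive rate for hypothesis ii.* It is not. It needs all 15 pairs tested without adjustment, which the protocol does not state, and it concerns MDP scores. The 0-10 rating goes to the ANOVA at about 5%.
- *That post-hoc tests are declared uncorrected.* This would rest on silence. The sentence applies only after a significant result, and the adjustment may be in an analysis plan that is not shown. The single P<0.05 threshold invites the question but does not settle it.
- *That the 15 pairs should be multiplied by the 11 MDP items.* The protocol also gives three subsections and does not say which level is tested.
- *That the most breathless participants drop out of the ANOVA.* Someone who stops early still has 10-second ratings and can complete the MDP. The protocol's completion figures (93% at 1.5 km/h, 84% at 2.5 km/h) come from a cited 3-minute walk on the flat, whereas Part B is a treadmill test on a gradient with 1.5 km/h stated. They do not yield a loss rate for Part B.

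It is also fair that lower power against a straight line is a matter of efficiency. A trend contrast within the ANOVA is not excluded, and where the rise is large the two tests hardly differ.

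**Conclusion.** The point holds in two parts of different weight. The named questionnaire test does not fit the six-gradient MDP data. If it is applied pair by pair at 0.05, the error per MDP score is about 38% for all 15 pairs or 18-21% for five, instead of 5%. These figures assume no gradient effect, equal correlations and two-sided tests; they barely changed with n or with the shape of the scores.

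The omnibus ANOVA for the dyspnea rating is valid. It is less efficient than a slope in every linear scenario tried, by up to about 25 percentage points, with little difference when power is already high and a gap of about 9 points when slopes vary strongly between people. These sizes rest on assumed effects, because the protocol gives no SD or target difference. The lack of an estimate per 1% gradient does not depend on those assumptions. This should be corrected, but it does not invalidate Part B.

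**What to change.** In the Data Analysis section, for Part B:

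- Make the primary test the linear slope of the dyspnea rating per 1% gradient, from a linear mixed model with random intercept and slope per participant and test order as a covariate. Report the slope with its 95% CI.
- Use the same model for the three MDP subsections in place of the Wilcoxon test, and keep that test for comparisons of two paired conditions. Three subsections still mean three tests, so say whether they are supportive or also adjusted.
- Holm-adjust any pairwise gradient comparisons.

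The cost is analysis wording; no visit or measurement changes. There are two downsides. The slope assumes near-linearity over 3-8%, which a quadratic term can check. If the last rating is used for tests stopped early, exercise durations are mixed and the slope may be flattened, so add a sensitivity analysis at a common time point.

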# • Study Objectives

#### Aims

The overarching aim of the current study is to develop a 2-minute walk treadmill test to evaluate dyspnea. The primary aims are to assess:

- i. the relationship between 6MWD and exertional dyspnea scores within a 6MWT when compared against exertional dyspnea scores recorded during the dyspnea challenge.
- ii. the sensitivity of the dyspnea challenge to changes in exertional dyspnea via changes to the gradient of the treadmill.
- iii. Compare the exertional dyspnea response to the dyspnea challenge in heart failure, pulmonary hypertension and COPD.
- iv. To assess the responsiveness of the dyspnea challenge to changes in exertional dyspnea experienced post an acute intervention and exercise rehabilitation programs (Pulmonary and Heart Failure rehabilitation programs).

Secondary aims, of the study, will be:

- v. To compare the metabolic cost of the 6MWT and the dyspnea challenge.
- vi. To compare the metabolic cost of the dyspnea challenge between cardiopulmonary disease populations.
- vii. Establish a minimally important difference (MID) for the dyspnea challenge.

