#### e. Outcome Measures

## 1. Primary outcome measure:

- a. Dyspnea (ED) -
  - Modified Borg 0-10 Scale A common measure taken during field-based testing. This will be measured using a 0-10 scale and does not involve any invasive procedures. This 0-10 scale has been used previously within COPD patients during the dyspnea challenge[25].
  - Multidimensional Dyspnea Profile (MDP): The MDP contains 11 items which participants rate on a continuous scale (0-10) and a forced-choice question for five sensory qualities [31]. The profile is split into three subsections; Sensory Dimension (SQ), Breathing Discomfort (A1) and Emotional Response (A2)[30]. This has been previously validated within clinical settings[32].
  - *Dyspnea*-12: A 12 descriptor item questionnaire that provides an overall score for breathlessness severity that matches the participants breathing 'these days'. It incorporates seven physical items and five affective items. Frequently used at baseline and during follow-up assessments[33].
  - Baseline and Transition Dyspnoea Index (BDI/TDI): The BDI/TDI measures the severity of breathlessness at the beginning of an intervention (BDI) then again at the end of the intervention (TDI). The questionnaire is comprised of three subsections; Functional Impairment, Magnitude of Task and Magnitude of Effort. This has been previously validated within clinical settings[34].

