## g. Translation to Changes in Clinical Practice

The primary aims for this study are to assess whether 6MWD is an adequate surrogate measure of exertional dyspnea and to assess the ability of the dyspnea challenge to monitor changes in dyspnea scores during increasing resistance of exercise. Clinically, exertional dyspnea is measured using poorly controlled or inadequate tests. Providing a test, that can be used clinically, that will induce exertional dyspnea and monitor changes in this symptom, allow for the individualised mechanisms and treatments to be effectively examined. Information gathered from such a test will allow for the creation of individualised symptom management strategies. With a resulting improvement in dyspnea symptoms and an increase in physical activity. Furthermore, this study answers the call for a challenge to be created in which allows for extended physiological factors to be measured allows for a comprehensive physiological characterisation for those who may have close to normal pulmonary function scores.

It is intended that the results from this study will be published in a peer reviewed journal. Results will also be disseminated locally within the relevant departments; The Prince Charles Hospital, Bundaberg Health Promotions, Central Queensland University and Griffith University. It is

proposed that the results will be presented at a respiratory or cardiac conference, although the conference has not been decided upon.

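### The protocol gives two different lists of primary aims and several primary dyspnea scores with none deciding, yet applies P<0.05 to every test

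*Protocol*

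**What the plan says.** **Primary aims.** The Aims section, under Study Objectives, says "The overarching aim of the current study is to develop a 2-minute walk treadmill test to evaluate dyspnea. The primary aims are to assess". Four items follow:
- (i) how 6MWD and 6MWT dyspnea relate to dyspnea in the challenge;
- (ii) sensitivity to gradient;
- (iii) comparison of the three diseases;
- (iv) responsiveness to an acute intervention and to rehabilitation.

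The synopsis has four broadly matching objectives. Section g (Translation to Changes in Clinical Practice) differs: "The primary aims for this study are to assess whether 6MWD is an adequate surrogate measure of exertional dyspnea". Its only other primary aim is how well the challenge follows dyspnea as exercise resistance rises. That covers only (i) and (ii).

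**Primary outcome.** Outcome Measures, item 1, has a singular heading. Under it stand the 0-10 rating, the MDP, Dyspnea-12 and BDI/TDI. Six-minute walk distance follows, before the secondary outcomes begin. On the MDP the section says "The profile is split into three subsections; Sensory Dimension (SQ), Breathing Discomfort (A1) and Emotional Response (A2".

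**Analysis.** Section f plans repeated-measures ANOVA with two within-subject factors, time and condition, and treats dyspnea scores the same way. Questionnaires get a Wilcoxon signed rank test, other comparisons are descriptive, and correlation statistics are optional. Post-hoc work follows any significant result. One threshold covers everything: "All statistical tests will be done with SPSS software with a significance threshold of P<0.05".

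**Hypotheses.** These refer to exertional dyspnea without naming a score, for example "The dyspnea challenge is able to detect both acute and longer term changes in exertional dyspnea as a result of interventions".

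**The concern.** Choosing the primary aims and the primary outcome is a protocol task, and here both are fixed badly. Disease comparison and responsiveness are primary in one section and absent from the list in another. Within an aim, several scores stand level with each other, and each may be tested at 0.05.

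Two consequences follow. First, hypothesis ii (gradient) or iv (responsiveness) could be declared supported because any one of several scores crossed the threshold, so the error rate behind that claim exceeds the stated 5%. Second, the scores can disagree. The binder might move the sensory subscore but not the 0-10 rating or the emotional response, and nothing says whether the challenge would then count as responsive. The synopsis intends the results to validate the test in these populations, so this ambiguity bears directly on the main conclusion.

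**Working it through.** The protocol states no family-wise error rate, so the only figure to start from is the threshold of 0.05.

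**Inputs**
- Threshold 0.05 per test (section f). Sidedness is not stated; two-sided is assumed.
- Comparisons that fit the two-within-factor design: gradient (Part B), binder on versus off (Part C), before versus after rehabilitation (Part C). That is 3.
- Scores per comparison: the 0-10 rating, which is the challenge's own measure (described in Parts A and B), plus MDP SQ, A1 and A2, since the MDP follows every test. That is 4.
- Left out: Dyspnea-12 is scheduled only at visit 1, TDI only at visit 9, and BDI at no visit.
- Correlation r between test statistics: not in the protocol; assumed from 0 to 0.9.

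**Formula.** For m tests with no true effect:
- Independent: 1 − 0.95^m.
- Equally correlated: each statistic is √r·G + √(1−r)·E, with G shared and E separate, both standard normal. The rate is 1 − the mean over G of [P(|Z| < 1.96 given G)]^m, obtained by numerical integration.

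**Results**

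| Tests | r = 0 | r = 0.5 | r = 0.8 | r = 0.9 |
|---|---|---|---|---|
| 2 (rating and one MDP score) | 9.8% | 9.1% | 7.8% | 7.0% |
| 4 (rating and three MDP subscores) | 18.5% | 15.6% | 11.4% | 9.4% |
| 12 (3 comparisons × 4 scores) | 46.0% | 31.9% | 18.6% | 13.5% |

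The independent values are 1 − 0.95^2 = 0.0975, 1 − 0.95^4 = 0.1855 and 1 − 0.95^12 = 0.4596.

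The last row uses one r both within and across comparisons. If scores correlate within a comparison but the three comparisons are independent, the 12-test rate is 1 − (1 − 0.1558)^3 = 39.8% at r = 0.5 and 1 − (1 − 0.0936)^3 = 25.5% at r = 0.9.

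**Not counted.** Six gradients allow 6 × 5 / 2 = 15 pairwise post-hoc contrasts per score. No correction is named for these, but they follow a significant overall test and are outside the table.

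**The case against.** A reader might infer that all four primary aims are tested on four scores each: 16 tests, with a family-wise rate of 1 − 0.95^16 = 56%, or about 37% at r = 0.5. The protocol does not support that count. Aim i is a relationship, for which section f offers only optional correlation statistics. Aim iii compares diseases, but the design has no between-group factor and other comparisons are descriptive. The 16-test figure counts tests that the plan does not specify.

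Nor do the face-mask conditions clearly double the Part A count. The mask-free tests are there to remove the mask's effect on dyspnea ratings, which points to their use for dyspnea.

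Three further objections deserve weight:
- The protocol does not say that the three MDP subscores will be tested separately. This stands, and is why the two-score row is shown. That row still exceeds 5%.
- The rates assume no effect anywhere, whereas Study Procedure describes the binder as known to worsen dyspnea and rehabilitation as known to improve it. This stands. The percentages measure how loose the decision rule is; they do not forecast a wrong conclusion. The lack of a deciding score does not depend on the null.
- Multiplicity rules are commonly left to a statistical analysis plan, which is not shown. Silence alone would therefore be no finding. But section f states a blanket rule and the aims contradict each other in the protocol itself, so those sections would still need amending.

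**Conclusion.** The point holds for what the protocol states: two conflicting lists of primary aims, several scores under one primary heading with none deciding, and P<0.05 for every test. For each of the three within-person comparisons, the false positive rate under a global null is about 9-19% with four scores and about 7-10% with two. Across the 12 tests it runs from 13.5% to 46%, and is 32% at r = 0.5. No single percentage should be quoted as the trial's error rate, because the correlations are assumed and two-sided tests are presumed. The ambiguity when scores disagree needs none of these assumptions. This should be corrected before analysis.

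**What to change.** 1. Reconcile the Aims section and section g to one list of primary aims.
2. Name the in-test 0-10 dyspnea rating as the single deciding score, with one summary value stated in advance. Use the mask-free tests for dyspnea in Part A.
3. Give each primary aim contrasts that fit it: a stated association for aim i; the gradient effect for aim ii; a between-disease comparison for aim iii, or label aim iii descriptive; the binder change and the rehabilitation change for aim iv. A single condition effect cannot serve aims i and iii.
4. Apply Holm across the primary contrasts. With all five, the smallest p-value is compared with 0.05/5 = 0.01; with aim iii descriptive, 0.05/4 = 0.0125. A fixed order at 0.05 would also do, provided responsiveness is not placed behind the aim i association.
5. Make MDP SQ, A1 and A2, Dyspnea-12 and TDI secondary or supportive. Keep 6MWD only as the comparator for aim i.

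With one prespecified test per contrast and Holm across them, the family-wise rate for primary claims is at most 5%. No participants, visits or measurements are added, though testing aim iii formally needs a model with a between-group factor. The downside is that MDP and questionnaire results can no longer be claimed as confirmatory, and Holm slightly lowers power per aim.

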## g. Translation to Changes in Clinical Practice

The primary aims for this study are to assess whether 6MWD is an adequate surrogate measure of exertional dyspnea and to assess the ability of the dyspnea challenge to monitor changes in dyspnea scores during increasing resistance of exercise. Clinically, exertional dyspnea is measured using poorly controlled or inadequate tests. Providing a test, that can be used clinically, that will induce exertional dyspnea and monitor changes in this symptom, allow for the individualised mechanisms and treatments to be effectively examined. Information gathered from such a test will allow for the creation of individualised symptom management strategies. With a resulting improvement in dyspnea symptoms and an increase in physical activity. Furthermore, this study answers the call for a challenge to be created in which allows for extended physiological factors to be measured allows for a comprehensive physiological characterisation for those who may have close to normal pulmonary function scores.

It is intended that the results from this study will be published in a peer reviewed journal. Results will also be disseminated locally within the relevant departments; The Prince Charles Hospital, Bundaberg Health Promotions, Central Queensland University and Griffith University. It is

proposed that the results will be presented at a respiratory or cardiac conference, although the conference has not been decided upon.

